3.3.1.6 Subject terminology convention

The term “Participant” is generally used to refer to language based on the CSP, vendor technology, patient-reported outcomes (PROs), and publication titles. The word “subject” is more commonly encountered in the statistical sections of this SAP for consistency with standard statistical terminology. Participant, patient, and subject are used interchangeably.

3.3.1.7 Summary statistics

Quantitative data will be summarised by descriptive statistics including number of subjects in category (n), mean, standard deviation (SD), minimum, first quartile (Q1), median, third quartile (Q3), and maximum. Geometric mean and coefficient of variation (CV) will be calculated in addition to arithmetic mean and SD, if appropriate.

Categorical data will be summarised as the number and percentage of subjects in each treatment group for each category. When appropriate, number of missing observations will be presented, and these will not be included in the denominator when calculating percentages.

A general rule is to present descriptive summary statistics (mean, SD, median, Q1, Q3) to 1 more decimal place than the individual values. The minimum and maximum values will be reported to the same number of decimal places as the individual values.

Absolute change from baseline will be presented in addition to absolute values. It will be summarised by descriptive statistics at the same timepoints as absolute values, except for baseline itself.

All confidence intervals (CIs) will be 95%.

3.3.1.8 Time at risk and censoring

If a subject has an event with onset day during the study period being analysed (see Section 3.3.1.5), it will be included in the analysis. For subjects with an event, the time at risk will be derived as

- *Event onset date – date of randomisation + 1 for FAS*
- *Event onset date – date of first date of IP + 1 for SAS*

For event-free subjects, the time at risk will be derived based on the study period being analysed, see the definition in Section 3.3.1.5. Event-free subjects are censored on the last day of the study period.

3.3.1.9 Unit conventions

- 1 year is defined as 365.25 days
- 1 month is defined as $365.25/12 = 30.4375$ days

3.3.2 Visit Window

Visit windows will be used for analysing visit-based data and are based on the target day for a scheduled visit, see Schedule of Activities in the CSP. The range of the windows for scheduled on-site assessments are shown in

Table 1.

The visit closest to the target day and within the visit window is assigned. This can be a scheduled or unscheduled assessment.

Table 1 Visit windows for on-site assessments

Scheduled assessment	Visit	Target Day	Visit window (days)
All endpoints			

Week 4	4	29	[2 ¹ , 57]
Week 12	6	85	[58, 99]
Week 16	8	113	[100, 141]
Week 24	9	169	[142, 211]
Week 36	10	253	[212, 294]
Week 48	11	336	[295, 350]
Week 52	12	365	>350

¹. The Week 4 visit window also includes post-dose vital signs assessments (VS7) taken on the day of randomisation, but after the baseline assessment.

The analysis visit window as defined in Table 1 will not be used for the Orthostatic blood pressure test at 12 weeks. Instead, the nominal visit number will be used for this assessment.

Analysis visit windows for **CCI** will be described in Sections 4.2.9.4 and 4.2.18.1. Baseline is defined in Section 3.3.1.1.

3.3.3 Handling of Scheduled and Unscheduled Visits

Unscheduled visits can be assigned to a visit window if closer to the target day than the scheduled visit or if there is no measurement from a scheduled visit in the window. If a patient has performed more than one unscheduled visit within a window, the assessment closest to the target day will be used.

In case of ties between scheduled or unscheduled visits located on different sides of the target day, the earlier assessment will be used. In case of ties located on the same side of the target day (i.e., more than one value for the same day but different time), the value with the earlier entry time will be used.

In case of two or more scheduled or unscheduled visits for assessments with the same purpose and with identical dates and times (including possibly missing times), the average value will be derived, and in case that the record is assigned for its respective analysis visit, the average value will be used for analysis. This will be done both for cases with multiple baseline values or with multiple post-baseline values with the same date and time.

In some instances, several assessments of a vital sign variable are scheduled at the same visit for different purposes, e.g., systolic blood pressure at Visit 3. In this situation, the measurement from

the assessment for only vital signs purposes would be used, unless this is missing. If it is missing, then the supine BP pre-orthostatic test measurement or the supine BP pre-6MWT would be used for the analysis (in that order).

3.3.4 Multiplicity/Multiple Comparisons

The formal hypotheses tests will address the treatment effect of AZD4831 versus placebo on the dual primary endpoints KCCQ Total symptom score (TSS) change from baseline at 16 weeks and 6-minute walk distance (6MWD) change from baseline at 16 weeks. Multiplicity across primary and secondary endpoints due to multiple tests will be accounted for according to a gatekeeping test strategy for alpha recycling. The strategy is applied to control the family-wise type I error rate of 5 % of an erroneous rejection of the null hypothesis (Burman, 2009) (FDA, 2017).

The comparison between pooled doses of AZD4831 and placebo is formally tested, unless the randomisation to the AZD4831 5mg treatment group is stopped during the study, in which case the comparison of AZD4831 2.5mg and placebo will be formally tested.

First, both dual primary endpoints are tested with Holm method. The p-values for KCCQ-TSS and 6MWD are sorted from lowest to highest, if the lowest p-value is rejected at $\alpha/2 = 0.025$, then the other endpoint is tested at full $\alpha = 0.05$. If both dual primary endpoints are rejected, then the full testing mass of 0.05 will be passed on to testing in the secondary endpoint family.

The secondary endpoint family will be tested within a fixed sequence in the order listed below:

1. KCCQ-TSS change from baseline at 24 weeks
2. KCCQ-TSS change from baseline at 48 weeks
3. 6MWD change from baseline at 24 weeks
4. 6MWD change from baseline at 48 weeks
5. Change from baseline in log-transformed NT-proBNP at 16 weeks
6. Change from baseline in log-transformed NT-proBNP at 24 weeks
7. Change from baseline in log-transformed NT-proBNP at 48 weeks
8. LV-GLS change from baseline at 16 weeks
9. LV-GLS change from baseline at 24 weeks

10. LAVI change from baseline at 16 weeks
11. LAVI change from baseline at 24 weeks
12. LVMI change from baseline at 16 weeks
13. LVMI change from baseline at 24 weeks
14. Change from baseline in log-transformed hsCRP at 16 weeks
15. Change from baseline in log-transformed hsCRP at 24 weeks
16. Change from baseline in log-transformed hsCRP at 48 weeks
17. Change from baseline in log-transformed IL-6 at 16 weeks
18. Change from baseline in log-transformed IL-6 at 24 weeks
19. Change from baseline in log-transformed IL-6 at 48 weeks

By this approach, full alpha is passed onto the next hypothesis in the sequence until a test fails to reject the null hypothesis or until all the listed null hypotheses are rejected. P-values from all endpoints in the hierarchy below the first non-rejected secondary endpoint and explorative endpoints are not adjusted, thus will be nominal and considered explorative.

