In Part A, participants will undergo a screening period of up to 4 weeks, followed by randomisation across 3 different treatment arms. Eligible participants will be randomised at a 1:1:1 ratio and dosed orally once daily. The planned treatment arms are AZD4831 2.5 mg, AZD4831 5 mg, and placebo. Participants will receive either AZD4831 or placebo for 16 weeks and then continue into a safety extension, during which they will receive an additional 32 weeks of the intervention (AZD4831 or placebo, as per their assigned arm during randomisation). A final follow-up visit (end of study visit) will occur at 52 weeks from randomisation. In the event that randomisation to the AZD4831 5 mg treatment arm is stopped during the study in either the whole study or in a country or specific ethnic population due to safety, the remaining participants in that cohort would be randomised at a 2:1 ratio to AZD4831 2.5 mg or matching placebo.

In Part B, participants will undergo a screening period of up to 2 weeks, followed by randomisation across 2 treatment arms. Eligible participants will be randomised at a 1:1 (AZD4831:placebo) ratio and dosed orally once daily. The planned treatment groups are AZD4831 at the dose selected based on Part A, and placebo. Participants will be treated for 24, 36 or 48 weeks, depending on when in time they were enrolled. The date of the last participant randomised in the study will determine the treatment period for patients who are still in the study. When the last patient is randomised, the end of the 24 week treatment period will be known; therefore the end of treatment date for all other ongoing participants will be scheduled in advance to occur at 24, 36 or 48 weeks. Consequently, earlier enrolment will allow a longer treatment period, whereas later enrolment will restrict the treatment period to 24 weeks. Participants will be treated for a minimum of 24 weeks to allow sufficient time for

efficacy evaluation, and a maximum of 48 weeks to assess longer-term safety and effect of the IP. A final end of study visit will occur 4 weeks after the final dose.

Participants can be randomised only once in the study; therefore, participants who were randomised into Part A cannot be included in Part B.

Data Monitoring Committee: Yes

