6.3 Measures to Minimise Bias: Randomisation and Blinding

All participants will be centrally assigned to randomised study intervention using an IRT/RTSM. This computerised randomisation procedure will ascertain allocation concealment and will assign the participants 1:1:1 to two dose levels of AZD4831 or matching placebo in Part A and 1:1 to AZD4831 or matching placebo in Part B. For Part A, in the event that randomisation to the AZD4831 5 mg treatment arm is stopped during the study due to safety in either the whole study or in specific countries or ethnic populations, the remaining participants in that cohort will be randomised at a 2:1 ratio to 2.5 mg AZD4831 or matching placebo.

The randomised study population will be capped by neutrophil count, 6MWD and KCCQ-TSS in both Part A and Part B. The capping will consist of:

- The proportion of participants having neutrophil count $> 4 \times 10^6/\text{mL}$ at Screening will be 60%-80%
- A maximum of 25% of the participants can have 6MWD ≥ 350 and ≤ 400 meters at randomisation visit.
- A maximum of 30% of the participants can have KCCQ-TSS > 80 and ≤ 90 at randomisation visit.

LVEF value at screening and atrial fibrillation/flutter status on ECG at Screening (Visit 1) may also be capped in the IRT/RTSM to avoid over- or under-representation of these participant subgroups.

The randomisation will be stratified by neutrophil count in both Part A and Part B.

The study will be blinded to both participants and Investigators/site staff as well as to the sponsor (designated sponsor personnel will be unblinded as part of DRC and URC in Part A as described in Appendix A 5). The IRT/RTSM will provide to the Investigator(s) the kit identification number to be allocated to the participant at the dispensation visit. Study intervention will be dispensed at the study visits summarised in the SoA (See Section 1.3). Routines for this will be described in the IRT/RTSM user manual that will be provided to each centre.

The randomisation code should not be broken except in medical emergencies when the appropriate management of the participant requires knowledge of the treatment randomisation. The investigator documents and reports the action to AZ, without revealing the treatment given to participant to the AZ staff.

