9.4 Statistical Analyses

The Statistical analysis plans will be finalised prior to database lock and it will include a more technical and detailed description of the statistical analyses described in this section. This section is a summary of the planned statistical analyses of the most important endpoints including primary and secondary endpoints.

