9.4.1 General Considerations

All personnel involved with the analysis of the study will remain blinded until database lock and protocol violations have been identified and documented. The only exception are study independent personnel who are involved in the interim analyses in Part A. Analyses will be performed by AZ or its representatives.

Nominal significance levels will be 0.05 and all tests performed will be two-sided. All confidence intervals will be 95%.

For Part A, baseline will be defined as the last non-missing value on or before the day of first dose and on or before the day of randomisation (whatever occurs first), individually for each participant and endpoint. The baseline value for safety analyses is the last non-missing value prior to administration of the first dose of IP.

In Part B, for subjects who receive first administration of IP on the day of randomisation, the baseline value for statistical analysis of safety parameters is the last non-missing value prior to the administration of the first dose of IP. For subjects where the first administration of IP takes place after the day of randomisation, the baseline is defined as relative to the day and timepoint of randomisation instead of actual day of first administration of IP.

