9.4.2 Efficacy

9.4.2.1 Primary Endpoint(s)

The primary efficacy endpoints are KCCQ-TSS and 6MWD and the primary efficacy variables are change from baseline in KCCQ-TSS and 6MWD at 16 weeks for Part A and at 24 weeks for Part B.

All primary variables will be analysed using ANCOVA with baseline and treatment group as covariate, and will be adjusted for the stratification factor for neutrophil count (Part A and Part B), comparing the AZD4831 doses versus placebo. For Part A, both single doses alone, and both doses pooled, will be compared with placebo. In Part B, a term for treatment by-baseline interaction will be included as independent variable in the model for KCCQ-TSS.

Model summary in Part A:

- 6MWD change from baseline at 16 Weeks:

$$\begin{aligned} E[CHG_{6MWD} | BASE_{6MWD}, TRT] \\ = \beta_0 + \beta_1 * BASE_{6MWD} + \beta_2 * STRATA + \beta_3 * TRT \end{aligned}$$

- KCCQ-TSS change from baseline at 16 Weeks:

$$\begin{aligned} E[CHG_{KCCQ-TSS} | BASE_{KCCQ-TSS}, TRT] \\ = \beta_0 + \beta_1 * BASE_{KCCQ-TSS} + \beta_2 * STRATA + \beta_3 * TRT \end{aligned}$$

Model summary in Part B

- 6MWD change from baseline at 24 Weeks:

$$\begin{aligned} E[CHG_{6MWD} | BASE_{6MWD}, TRT] \\ = \beta_0 + \beta_1 * BASE_{6MWD} + \beta_2 * STRATA + \beta_3 * TRT \end{aligned}$$

- KCCQ-TSS change from baseline at 24 Weeks:

$$\begin{aligned} E[CHG_{KCCQ-TSS} | BASE_{KCCQ-TSS}, TRT] \\ = \beta_0 + \beta_1 * BASE_{KCCQ-TSS} + \beta_2 * STRATA + \beta_3 * TRT + \beta_4 \\ * BASE_{KCCQ-TSS} * TRT \end{aligned}$$

Where TRT indicates randomized treatment group; STRATA indicates neutrophil baseline strata; BASE_{6MWD} and CHG_{6MWD} indicates baseline and change from baseline in 6MWD, respectively; and BASE_{KCCQ-TSS} and CHG_{KCCQ-TSS} indicates baseline and change from baseline in KCCQ-TSS, respectively.

Subgroup analyses will be performed for both primary endpoints.

Primary Efficacy Objectives Related Estimands:

Part A:

Treatment: Treatment with 2.5 mg or 5 mg AZD4831 compared to placebo, administered in addition to optimal back-ground therapy for co-morbidities.

Population: Patients that fulfill all of the inclusion criteria, none of the exclusion criteria and have available measurements of the efficacy endpoint at baseline and 16 weeks.

Endpoint: Change from baseline to 16 weeks in KCCQ-TSS and 6MWD.

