2 CHANGES TO PROTOCOL PLANNED ANALYSES

A standard deviation of 20 points was assumed for KCCQ-TSS for the sample size calculations. No other changes to planned analyses.

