4.2.2.6 Supplementary Analyses of the Primary Endpoint

See Section 4.2.1.6 for details. For the fourth supplementary analysis, the ANCOVA model will include treatment group and neutrophil count stratum as categorical covariates, and the baseline value as continuous covariate. The figure described for the KCCQ-TSS fourth supplementary analysis in Section 4.2.1.6 will not be presented for this analysis.

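### If 5 mg randomisation is stopped study-wide, the formal test in SAP 3.3.4 moves to a contrast whose allocation changes mid-trial, and the protocol's ANCOVA has no term for the allocation scheme

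*SAP*

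**What the plan says.** Part A randomises 1:1:1 to 2.5 mg, 5 mg and placebo. Protocol 6.3 provides that, if the 5 mg arm is stopped for safety, "the remaining participants in that cohort will be randomised at a 2:1 ratio to 2.5 mg AZD4831 or matching placebo". The Synopsis (1.1) describes the same contingency for the case where the 5 mg arm "is stopped during the study in either the whole study or in a country or specific ethnic population due to safety".

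SAP 3.3.4 makes pooled doses versus placebo the formally tested comparison, "unless the randomisation to the AZD4831 5mg treatment group is stopped during the study, in which case the comparison of AZD4831 2.5mg and placebo" becomes the formal test. The two primary endpoints, KCCQ-TSS and 6MWD at 16 weeks, go through Holm's procedure with a first step at 0.025, and the SAP claims family-wise control at 5%.

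On the model, Protocol 9.4.2.1 says the primary variables "will be analysed using ANCOVA with baseline and treatment group as covariate, and will be adjusted for the stratification factor" for neutrophil count. The Part A equations there contain baseline, stratum and treatment only. SAP 2 records a corrected KCCQ-TSS standard deviation and then states "No other changes to planned analyses". The one full covariate list that can be read in the SAP, in 4.2.2.6, belongs to a supplementary 6MWD analysis and matches the protocol: "the ANCOVA model will include treatment group and neutrophil count stratum as categorical covariates, and the baseline value as continuous covariate".

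**The concern.** When allocation between two arms changes during recruitment, the arms contain different proportions of early and late participants. If late participants differ in mean change for reasons unrelated to treatment, part of that difference is read as a treatment effect.

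The pooled contrast is immune. Placebo receives one third of participants before and after a stop, so pooled active to placebo remains 2:1. The 2.5 mg contrast is not immune. The SAP therefore moves the formal test from a contrast with constant allocation to one with changing allocation, without a matching change in any model that can be read. Adjustment for baseline score and neutrophil stratum removes only the drift carried by those two variables. What is at stake is the error control claimed in SAP 3.3.4, in this branch and for Part A only.

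**Working it through.** **Inputs.** From Protocol 9.2: 660 randomised, about 600 with complete data, 200 per arm, 6.0 points and critical value 3.9 for KCCQ-TSS, 21 m and 14 m for 6MWD, 6MWD SD 70 m. From SAP 2: KCCQ-TSS SD 20 (Protocol 9.2 prints 18). From SAP 3.3.4: first-step alpha 0.025, two-sided (z = 2.241). Assumed, because the documents give no figure: the timing of the stop, and D, the difference in mean change between participants randomised after and before the stop that remains after covariate adjustment.

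**The plan's own figures.** KCCQ-TSS with SD 20: SE = 20 × √(2/200) = 2.0; critical value 1.96 × 2.0 = 3.92; power for 6 points = Φ(6/2.0 − 1.96) = 85.1%. 6MWD: SE = 70 × √(2/200) = 7.0; critical value 13.7 m; power for 21 m = 85.1%. These match the plan. SD 18 does not (power 91.5%, critical value 3.53), so SD 20 is used below.

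**Imbalance after a study-wide stop.** Let x be the share of all participants randomised after the stop. That share is x in placebo and 2x/(1+x) in the 2.5 mg arm, so the fraction of D that enters the estimate is

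w = 2x/(1+x) − x = x(1−x)/(1+x).

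- Stop at 25% of accrual (x = 0.75): w = 0.107
- Stop at 50% (x = 0.50): w = 200/300 − 100/200 = 0.167
- Stop at 75% (x = 0.25): w = 0.150
- Maximum, at x = 0.414: w = 0.172

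**Type I error, stop at half accrual, no scheme term.** Completers are 300 on 2.5 mg (100 before, 200 after) and 200 on placebo (100 + 100). True SE = 20 × √(1/300 + 1/200) = 1.826. The fitted SD absorbs part of D: √(400 + D² × (300 × 0.2222 + 200 × 0.25)/500). The error is the probability that an estimate distributed N(0.167D, 1.826²) exceeds 2.241 fitted SEs in absolute value.

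| Endpoint | D | Bias (0.167D) | Error at nominal 2.5% |
|---|---|---|---|
| KCCQ-TSS, SD 20 | 0 | 0 | 2.5% |
| KCCQ-TSS, SD 20 | 2 points | 0.33 | 2.7% |
| KCCQ-TSS, SD 20 | 5 points | 0.83 | 3.9% |
| 6MWD, SD 70 | 10 m | 1.7 m | 3.0% |
| 6MWD, SD 70 | 20 m | 3.3 m | 4.35% |

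For KCCQ-TSS at D = 5, stops at 25% and 75% of accrual give 3.1% and 3.5%. A simulation of 20,000 trials gave 2.6/2.6/3.9% for D = 0/2/5 without the scheme term and 2.4/2.7/2.5% with it.

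**Partial stop, if it triggered the switch.** Suppose 5 mg is stopped halfway through recruitment in a country holding 5%, 10% or 20% of participants. The shares randomised 2:1 are 10/205 vs 5/200, 20/210 vs 10/200 and 40/220 vs 20/200, so w = 0.024, 0.045 and 0.082. The error at D = 5 is 2.5%, 2.6% and 2.8%.

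**The case against.** The strongest objection is that the model evidence is incomplete. SAP 4.2.1.4 and 4.2.1.5 are not in the text available for review, the list in 4.2.2.6 concerns a supplementary analysis, and Protocol 9.4 says of the SAP that "it will include a more technical and detailed description of the statistical analyses described in this section". A scheme term could be there, and the statement in SAP 2 does not rule out added detail. This stands: a reader might infer that the SAP omits the term, but all that can be shown is that the protocol's explicit model lacks it and that no readable SAP text adds it.

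A second objection is that D has no source. Five points left after baseline adjustment is close to the whole 6-point target. The widening of KCCQ-TSS entry from 80 to 90 points in Amendment 3 acts on a variable already in the model. This also stands as a limit on size. The same amendment did change the NT-proBNP entry thresholds, which the model does not cover. That shows the recruited population can shift during the trial, but not that D reaches 5 points.

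Third, no stop is reported, a stop would be for safety rather than efficacy, and Protocol 4.1 has Part B analysed on its own participants only. All true, and the claim is limited accordingly.

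A reader might also infer from SAP 3.3.4 that a stop in one country would remove 5 mg from the formal test for the whole trial. The documents do not support that as the natural reading. Protocol 1.1 and 6.3 reach a partial stop only through an express qualifier, which SAP 3.3.4 lacks, and Table 3 in Protocol 2.3.1 lists stopping the arm and stopping in particular countries or ethnic populations separately. After a one-country stop, randomisation to 5 mg continues elsewhere. The sentence most naturally means a study-wide stop; making that explicit is a wording matter.

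**Conclusion.** The concern holds for a study-wide stop. The switched contrast has changing allocation, and the only primary model that can be read does not account for it. The effect is modest: at most about 17% of D, and at half accrual an error of 2.7% (D = 2) to 3.9% (D = 5) against a nominal 2.5% for KCCQ-TSS at SD 20. There is no bias if there is no stop or if D is zero. The figures assume 600 completers, proportional loss across arms and an assumed D.

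This does not show that the trial's error rate is inflated as things stand. It shows that one pre-specified branch relies on an unstated assumption of no residual drift, and that a better analysis is available at very small cost. For partial stops the bias is close to nil, and only the scope of the trigger needs stating.

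**What to change.** In SAP 3.3.4 and in the efficacy ANCOVA, state that if 5 mg randomisation is stopped, the switched test includes a two-level fixed effect for the allocation scheme under which each participant was randomised (1:1:1 or 2:1). If SAP 4.2.1.4 already has this term, a cross-reference is enough.

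Add a phrase to SAP 3.3.4 saying whether the switch applies only to a study-wide stop or also to a stop in a country or ethnic population. If partial stops are included, the 2:1 level should be participants randomised after the stop in the affected population. A plain country indicator would not do, because the ratio changes within the country.

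The cost is two sentences, no new data and one degree of freedom. For a stop at half accrual, SE with the term = 20/√(100×100/200 + 200×100/300) = 1.852 against 1.826, a rise of 1.4%. Power for 6 points at alpha 0.05 falls from 90.8% to 90.0%.

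Protocol 9.4.1 says "All personnel involved with the analysis of the study will remain blinded until database lock", with an exception for the independent staff running the Part A interim analyses, so blinded staff can make the change. Under SAP 5 the unblinded reviews begin once at least 150 participants could have reached Week 16. The wording should be settled by people who have seen no unblinded result.
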